8 STATISTICAL CONSIDERATIONS

This section describes the statistical methods to be used to analyze the efficacy and safety endpoints. Safety related analyses are described in Section 9. Full details will be provided in a formal statistical analysis plan (SAP). The final Clinical Study Report will describe deviations from the SAP, if any.

The statistical analyses will be done once all subjects have completed Week 96 (Week 96 visit or earlier if withdrawn).

8.1 SAMPLE SIZE AND POWER

 this required sample size is increased to 220 per group or a total randomized of 440.

8.2 GENERAL ANALYSIS CONVENTION

Unless otherwise stated, all analyses will be performed using SAS Version 9.4 or higher and the primary hypothesis test on relapses will be conducted at the two-sided type I error set to 0.05. All tertiary hypotheses will be conducted at a two-sided significance level of 0.05. P-values will be presented with 4 decimals and p-values that are less than 0.0001 will be presented as <0.0001.

Continuous (non-survival related) data will be summarized using descriptive statistics: number of observations (n), mean, standard deviation (SD), median, 25th and 75th percentiles, minimum, and maximum. Frequencies and percentages will be used to summarize categorical (discrete) data. Presentations of categorical data will generally suppress percentages for items where the count is zero in order to draw attention to the nonzero counts.

8.3 STATISTICAL ANALYSES WILL BE DESCRIBED IN DETAIL IN THE STATISTICAL ANALYSIS PLAN COMPLETED PRIOR TO FINAL DATA LOCK.ANALYSIS POPULATIONS

8.3.1 SAFETY POPULATION

The Safety Population will include all subjects who receive at least one dose of study drug (ublituximab or teriflunomide, with corresponding placebos). All safety assessments including toxicity will be performed on the Safety Population by treatment actually received.

8.3.2 INTENTION-TO-TREAT (ITT)

The Intention-to-Treat (ITT) population will consist of all randomized subjects. Subjects will be analyzed by randomized treatment group. Analyses of key efficacy endpoints based on ITT population will serve as sensitivity analyses.

8.3.3 MODIFIED INTENTION-TO-TREAT (MITT)

The modified Intention-to-Treat (mITT) population will consist of all subjects in the ITT population who received at least one dose of study medication and have at least one baseline and post baseline efficacy assessment. The primary efficacy analyses will be performed based on the mITT population.

The MRI analyses will be based on the subset of subjects in the mITT population who have one baseline and post-baseline MRI efficacy assessment.

Subjects will be analyzed by randomized treatment group.

8.3.4 PER-PROTOCOL GROUP (PP)

The Per-Protocol (PP) population will consist of all subjects in the mITT group who were treated for at least 1.75 years and do not have a major protocol deviation that might impact efficacy analysis. The Per-Protocol population will only be used for sensitivity analysis of the primary efficacy and key secondary variables. Subjects will be analyzed by randomized treatment group.

8.4 SUBJECT DISPOSITION

8.4.1 SCREENING AND ENROLLMENT

Enrollment will be summarized by treatment group. A table will present the number and percentages of subjects by treatment group. Details include number of subjects screened, number of screening failures with reason and number of subjects enrolled.

8.4.2 DISPOSITION

The disposition of subjects (number randomized, treated, study medications exposure, duration of follow-up, subjects' allocation by country & region) will be tabulated by treatment group. Discontinuation of study medications prior to the end of study will be summarized by treatment group and reason for discontinuation will be displayed. Drug discontinuation and termination from study prior to the end of the study will be summarized by treatment group and reason for discontinuation and/or withdrawal (termination) will be displayed. Listings will present time to and

reason for discontinuation or termination by treatment group and subject. In addition, a table of major protocol deviations will be presented by group.

8.5 SUBJECT DEMOGRAPHICS AND BASELINE CHARACTERISTICS

Baseline demographic and clinical characteristics will be summarized as percentages for categorical variables and as mean, standard deviation, median, minimum and maximum for continuous measures. The analyses of baseline characteristics will be presented for the Safety, ITT, mITT, and PP Populations by treatment group.

8.6 MEDICAL HISTORY

Medical history will be captured at the Screening visit. Medical history will be coded using MedDRA and will be listed and summarized by MedDRA system organ class and preferred term for the Safety population.

All prior and concomitant medications and procedures will be classified by preferred terms according to the World Health Organization (WHO) Drug Dictionary and will be summarized by the number and percentage of subjects by preferred term. Prior medications and procedures are those which have a stop date prior to the randomization date, and concomitant medications and procedures are those which have a stop date after treatment start date or are ongoing. Concomitant medications will be assessed at both scheduled and unscheduled visits.

8.7 EXTENT OF EXPOSURE

The dose (mg) of study drugs administered, the total number of doses of study drugs, and the duration of treatment will be summarized with descriptive statistics.

For ublituximab or IV placebo infusions, treatment exposure is summarized as the total number of infusions (greater than 50% complete) received over the 5 expected infusions. Furthermore, the overall number of infusions, number and percentage (based on all infusions) of infusions completed with/without interruption and infusions not completed will be calculated per arm. The number and percentage of patients (based on all patients with at least one infusion) with and without any infusion complication (interruption or stop) per arm will be presented as well. The percentage of planned total infusion received will also be calculated.

For teriflunomide or oral placebo, the proportion of at least 80 percent of taken oral medication will be calculated. These proportions will be summarized by treatment group.

8.8 INTERIM SAMPLE SIZE REASSESSMENT

An independent committee, Blinded Assessment Relapse Team (BART), reporting to TG Therapeutics, and the DSMB will reassess the sample size for the study when 210 of the 220 participants have been randomized. Assuming a uniform rate of recruitment, we need an estimate as to how many person years of exposure will occur before an interim adjustment occurs. If

recruitment is going to be accomplished in 8 to 10 months, the average exposure time when 210 subjects per group are recruited would experience half of the recruitment period or $9/2=4.5$ months. We can use all of the data available at that time and thus will have approximately $4.5 \times 210 = 945$ person months or approximately 43 person years of observation (the denominator to compute the ARR).

The Table below provides the sample sizes (total adjusted sample sizes) needed per group per study based on the findings at the interim (Columns of the Table) for reductions in the ARR of teriflunomide by 40%. As an example, if the estimated ARR in the pooled population is 0.20 and we are assuming an hypothesized 40% reduction in the ARR rate by ublituximab, then the ARR in the individual groups (red numbers in the table below) can be derived by solving a simple equation; $(N_U * 0.6 P_T + N_T * P_T) / (N_U + N_T) = 0.20$ where P_T is the ARR in the teriflunomide group and N_T and N_U are the sample sizes, assumed to be equal. Thus, if the combined ARR=0.20, then this equation under the hypothesized reduction of 40% yields an estimated ARR of 0.25 in teriflunomide and 0.15 in ublituximab. Calculating the required sample size using a negative binomial comparison with 1.75 years of observation overall, results in an updated sample size of 219 per group. Thus, the original sample size of $N=200$ would be adjusted upward by adding 19 participants per treatment group, plus the 10% for dropouts yielding a total of 241 subjects per group or 21 additional participants.

In the Table below, which can guide the interim sample size reassessment, we see two color blocks in the table. The green area shows results that have two (2) characteristics - one, they require smaller sample sizes and two, they are unlikely to occur because the ARR rate in the teriflunomide group would have to exceed 0.31 (arbitrarily chosen, but some level is reasonable as an upper limit on what the rate is likely to be). Either way, if the blinded ARR falls in the green area or above, the sample size will not be reduced since we do not plan to reduce the sample size and 210 participants per group will have already been enrolled. The yellow area is the range for the combined total rates. If the overall ARR =0.19 then the estimated teriflunomide rate would be estimated at 0.2375 and ublituximab would be estimated at 0.1425 and the sample size required would be 233 per group. Thus, a rate ≤ 0.19 , the sample size will be increased by 30 per treatment group in each study, but no more. Such observed relapse rates are quite low and unexpected, so that further adjustments are probably not warranted.

Recruitment will continue while the interim analysis is ongoing and if the participants recruited beyond the 220 per group will be used in the final analyses if the sample size is not increased and will count toward the additional sample size if warranted.

% Reduction in ARR	Treatment	Findings at Interim findings at interim								
		0.160	0.180	0.200	0.220	0.240	0.260	0.280	0.290	0.300
40%	Ublituximab /oral placebo	0.120	0.135	0.150	0.165	0.180	0.195	0.210	0.218	0.225
	Teriflunomide/IV placebo	0.200	0.225	0.250	0.275	0.300	0.325	0.350	0.363	0.375
Avg Follow-Up = 1.75 years	N	268	243	224	208	195	183	174	169	165

8.9 EFFICACY ANALYSES

The primary efficacy endpoint will be tested at a two-sided Type I error of 5%. If the null hypothesis on the primary efficacy endpoint is rejected, the null hypotheses on the secondary efficacy endpoints will be tested. The key secondary outcomes will be tested using a hierarchical approach with the order specified as in the objectives using a step-down procedure where each test is a Type I error 0.05 (see Section 8.9.2).

For subjects who have withdrawn consent from the study, all data compiled up to the point of withdrawal will be used for analysis. For subjects who withdraw from their active treatment will not have the blind broken and all data up to the time of withdrawal from treatment will be used in the primary analysis. Sensitivity analyses will use all their data over the entire study period. Subjects who are withdrawn prematurely from study treatment will be included in all analyses regardless of the duration of treatment. Subjects who withdraw before they receive study medication they will be replaced, with new subjects who will be assigned new randomization numbers. If subjects withdraw prematurely from treatment, the subject will not be replaced. There will be no imputation for missing data except where sensitivity analyses are conducted.

8.9.1 PRIMARY EFFICACY VARIABLE

The primary efficacy variable will be Annualized Relapse Rate, defined as the number of relapses (protocol defined and confirmed by Independent Relapse Adjudication Panel) per subject-year (a year is equal to 365.25 days).

The primary efficacy analysis will be performed using the mITT with a Negative Binomial regression model to accommodate the potential over-dispersed data appropriately. The model will include the total number of confirmed relapses with onset between randomization date and the day of last study treatment as response variable, treatment group, EDSS strata (baseline EDSS score ≤ 3.5 versus > 3.5) and clinic region as covariates.

Relapses that occur after study drugs are withdrawn will be assessed over the remainder of the study period and this data will be utilized as part of additional sensitivity analysis (described in the statistical plan) as long as the subject has not withdrawn their consent to be in the trial.

The treatment group will have 2 levels (teriflunomide/ IV placebo or ublituximab/oral placebo). In order to account for different treatment durations among subjects, the log-transformed standardized treatment duration (randomization to date last treatment before early withdrawal or completion of Week 96 assessment) will be included in the model as an “offset” variable for appropriate computation of the Annualized Relapse Rate. [REDACTED] will be used to assess the overall model with subjects in a repeated statement using a Generalized Estimating Equation (GEE) approach.

Two-sided 95% confidence intervals of the rate ratio will be provided for the comparisons of Ublituximab/oral placebo versus teriflunomide/IV placebo. The estimated relapse rate and its 2-sided 95% confidence intervals will be provided for each treatment group.

8.9.2 SECONDARY EFFICACY VARIABLES

The key secondary outcomes will be tested using a hierarchical approach with the order specified below using a step-down procedure where each test is at a Type I error 0.05. If any endpoints fail to reach significance, then formal testing of significance of the subsequent secondary outcomes will not be performed.

1. Total number of gadolinium enhancing (Gd-enhancing) T1-lesions per MRI scan by Week 96.
2. Total number of new and enlarging T2 hyperintense lesions (NELs) per MRI scan by Week 96.
3. Time to Confirmed Disability Progression (CDP) for at least 12 weeks occurring during the 96-week, double-blind treatment period. *
4. Proportion of subjects with No Evidence of Disease Activity (NEDA) from Week 24 to Week 96.
5. Proportion of subjects reaching impaired SDMT (Symbol Digit Modalities Test) from baseline to Week 96.
6. Percentage change in Brain Volume from baseline to Week 96.

* Confirmed Disability Progression for at least 12 weeks during the 96-week treatment period will be analyzed using pooled data from the two identical studies TG1101-RMS301 and TG1101-RMS302.

The total number of gadolinium enhancing (Gd-enhancing) T1-lesions will be calculated as the sum of the individual number of lesions at weeks 12, 24, 48, and 96, divided by the total number of MRI scans of the brain. The total number of new and enlarging T2 hyperintense lesions will be calculated as the sum of the individual number of lesions at weeks 24, 48, and 96, divided by the total number of MRI scans of the brain. The MRI count variables will be assessed for differences between the treatment groups using negative binomial regression with an offset based on time on study and covariates, region, baseline EDSS strata, and baseline MRI counts. Percent brain volume change will be assessed between the two groups using linear mixed effects models [REDACTED] with covariates region, baseline EDSS strata, and baseline brain volume.

Disability progression is defined as an increase of ≥ 1.0 point from the baseline EDSS score that is not attributable to another etiology (e.g., fever, concurrent illness, or concomitant medication) when the baseline score is 5.5 or less, and ≥ 0.5 when the baseline score is above 5.5. Disability progression is considered confirmed when the increase in the EDSS score is confirmed at regularly scheduled visits at least 12 or 24 weeks after the initial documentation of neurological worsening.

Please note that Confirmed Disability Progression for at least 12 weeks during the 96-week treatment period will be analyzed using pooled data from the two identical studies TG1101-RMS301 and TG1101-RMS302. With the exception of this endpoint (CDP), which will be analyzed at the pooled level, all other secondary efficacy endpoints will be tested if and only if the individual study secondary endpoint listed ahead of it has reached the significance level at 0.05.

All pre-specified pooled analyses are listed below. However, only CDP for at least 12 weeks is part of the secondary analysis and the remainder are included in the tertiary analysis.

1. Time to Confirmed Disability Progression for at least 12 weeks (secondary analysis)
2. Time to Confirmed Disability Progression for at least 24 weeks (tertiary analysis)
3. Time to Confirmed Disability Improvement for at least 12 weeks (tertiary analysis)
4. Time to Confirmed Disability Improvement for at least 24 weeks (tertiary analysis)

Summary tables of progression to CDP will present the proportion who achieved CDP at Week 96 and associated 95% CIs for each treatment group. The median time-to-event with 2-sided 95% CIs as well as the proportion of subjects remaining event-free at times of interest will be estimated using Kaplan-Meier methods implemented with [REDACTED]. All time to CDP (and CDI) endpoints will be analyzed similarly.

The proportion of subjects with No Evidence of Disease Activity (NEDA) will be calculated at Week 96. A subject with NEDA is defined as a subject without relapses confirmed by the IRAP, without MRI activities (no T1 Gd+ lesions and no new/enlarging T2 lesions), and no 12-week Confirmed Disability Progression. Any evidence of disease activity from Week 24 to Week 96 will be counted as not reaching NEDA. Any evidence of disease activity before Week 24 will not count. NEDA rates will be compared using logistic regression [REDACTED] with baseline adjustments the same as used in the primary analysis plus baseline MRI counts and without an offset to take into account time on study.

Change in cognition (SDMT) will be assessed using the total score at each SDMT visit which is defined as the total number of correct answers reported in the CRF. Impaired SDMT is defined as a decrease from baseline of at least 4 points at any post-baseline assessment up to the Week 96 visit. The proportion of impaired SDMT will be analyzed in all subjects in the mITT population. SDMT rates will be compared using logistic regression [REDACTED] with baseline adjustments the same as used in the primary endpoint analysis, without treatment duration offset, but including log-transformed baseline MRI counts (T1 unenhancing, T2, Gad enhancing). To avoid zero values for the log transformation of MRI counts, 1 will be added to each observation before transforming.

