--	---

	
20. Other significant concurrent, uncontrolled medical condition including, but not limited to, cardiac, renal, hepatic, hematological, gastrointestinal, endocrine, immunodeficiency syndrome, pulmonary, cerebral, psychiatric, or neurological disease which could affect the subject's safety, impair the subject's reliable participation in the trial, impair the evaluation of endpoints, or necessitate the use of medication not allowed by the protocol, as determined by the PI of the trial
 
21. Current participation in any other interventional clinical trial. Participation in non-interventional trial requires approval by the Sponsor
 
22. Inability or unwillingness to comply with study and/or follow-up procedures outlined in the protocol
 
23. Lack of immunity to varicella as determined by screening based on the level of VZV IgG. Subject may receive vaccine and be rescreened
 
24. Vaccination with live virus within 2 months of randomization
 
25. History or presence of malignancy (except for surgically excised basal or squamous cell skin lesions), lymphoproliferative disease, or history of total lymphoid irradiation or bone marrow transplantation

Populations
	
The Intention-to-Treat (ITT) population will consist of all randomized subjects. Subjects will be analyzed by randomized treatment group.
 
Modified Intention to Treat (mITT) Population – all subjects in the ITT population who received at least one dose of study medication and have one baseline and post-baseline efficacy assessment.
 
For analysis of MRI endpoints, the subgroup of mITT subjects who have baseline and post-baseline MRI will be used.
 
The Safety Population will include all subjects who receive at least one dose of study drug (ublituximab or teriflunomide, with corresponding placebos).

Statistical Considerations
	
All efficacy analyses will be performed on the mITT population. The ARR will be analyzed using a Negative Binomial regression testing for treatment differences between UTX and teriflunomide, adjusted by region and baseline EDSS score as covariates. A significant result at a two-sided alpha=0.05 will demonstrate a superior effect of UTX in reducing ARR compared with teriflunomide. Further details on the planned statistical analysis and hypothesis to be test will be provided in the Statistical Analysis Plan.

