2.2 SECONDARY ENDPOINTS

The key secondary outcomes will be tested using a hierarchical approach with the order specified below using a step-down procedure where each test is at a Type I error 0.05. If any endpoint fails to reach significance, then formal testing of significance of the subsequent secondary outcomes will not be performed. The hierarchical analyses of the key secondary endpoints are as follows:

1. Total number of gadolinium enhancing (Gd-enhancing) T1-lesions per MRI scan by Week 96.
2. Total number of new and enlarging T2 hyperintense lesions (NELs) per MRI scan by Week 96.
3. Time to Confirmed Disability Progression (CDP) for at least 12 weeks occurring during the 96-week double-blind treatment period.*
4. Proportion of subjects with No Evidence of Disease Activity (NEDA) from Week 24 to Week 96.
5. Proportion of subjects reaching impaired SDMT (Symbol Digit Modalities Test) from baseline to Week 96.
6. Percentage change in Brain Volume from baseline to Week 96.

* Confirmed Disability Progression for at least 12 weeks during the 96-week treatment period will be analyzed using pooled data from the two identical studies TG1101-RMS301 and TG1101-RMS302.

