## 2.4.3 Secondary Endpoints

### 2.4.3.1 Statistical testing Strategy

Once the null hypothesis of the primary analysis has been rejected, the key secondary outcomes will be tested using a hierarchical approach with the order specified below using a step-down procedure where each test is at a Type I error 0.05. If any endpoint fails to reach significance, then formal testing of significance of the subsequent secondary outcomes will not be performed. All p-values will be reported and will be interpreted as either confirmatory or non-confirmatory (i.e., descriptive only).

[figure not shown]
1. Total number of gadolinium enhancing (Gd-enhancing) T1-lesions per MRI scan by Week 96.
2. Total number of new and enlarging T2 hyperintense lesions (NELs) per MRI scan by Week 96
3. Time to confirmed disability progression (CDP) for at least 12 weeks occurring during the 96-week, double-blind, treatment period (pooled analysis with Study TG1101-RMS302). \*
4. Proportion of subjects with no evidence of disease activity (NEDA) from Week 24 to Week 96.
5. Proportion of subjects reaching impaired SDMT (Symbol Digit Modalities Test) from baseline to Week 96.
6. Percentage change in Brain Volume from baseline to Week 96.

\* Confirmed Disability Progression for at least 12 weeks during the 96-week treatment period will be analyzed using pooled data from the two identical studies TG1101-RMS301 and TG1101-RMS302.

For all tests other than #3 (12-week CDP), the testing will be based on Study ULTIMATE II individually, at  $\alpha=0.05$ .

For #3, 12-week CDP endpoint, the testing will be based on pooled data from both Studies ULTIMATE I and ULTIMATE II achieve sufficient statistical power to detect relevant treatment differences. Therefore, this test will not be performed until data from both studies are available. Specifically, this test is considered confirmatory only if all tests for the primary endpoint and all secondary endpoints before this test (i.e. #1 & #2) are statistically significant at  $\alpha=0.05$  level in both studies. Once this test is statistically significant, all subsequent tests (#4-6) will continue at  $\alpha=0.05$  level within each individual study.

The statistical testing sequence is illustrated below.

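### Does Protocol 8.9.2 let NEDA, SDMT and brain volume be tested formally after pooled disability progression has failed?

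*Protocol*

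**What the plan says.** Protocol 2.2 lists six key secondary endpoints in order: Gd-enhancing lesions (1), new or enlarging T2 lesions (2), 12-week CDP (3), NEDA (4), SDMT impairment (5) and brain volume change (6). It adds the stop rule: "If any endpoint fails to reach significance, then formal testing of significance of the subsequent secondary outcomes will not be performed". The opening of Protocol 8.9.2 repeats it: "If any endpoints fail to reach significance, then formal testing of significance of the subsequent secondary outcomes will not be performed". Protocol 8.9 places the primary endpoint in front of the whole list.

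Further down in 8.9.2, after a sentence stating that CDP is analysed on pooled data, the protocol continues: "With the exception of this endpoint (CDP), which will be analyzed at the pooled level", and then "all other secondary efficacy endpoints will be tested if and only if the individual study secondary endpoint listed ahead of it has reached" the 0.05 level.

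SAP 2.4.3.1 restates the order and the stop rule. On CDP it says that "this test is considered confirmatory only if all tests for the primary endpoint and all secondary endpoints before this test" (items 1 and 2) are significant at the 0.05 "level in both studies. Once this test is statistically significant, all subsequent tests (#4-6) will continue at" 0.05 within each study. The protocol does not state the both-studies condition. The protocol synopsis hands the detail to the SAP: "Further details on the planned statistical analysis and hypothesis to be test will be provided in the Statistical Analysis Plan". Protocol 8 does the same, and says that the study report will describe deviations from the SAP.

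**The concern.** The endpoint immediately ahead of NEDA is CDP, and CDP is pooled. Taken literally, the last individual-study endpoint ahead of NEDA is therefore item 2. On that reading NEDA, then SDMT, then brain volume could be tested formally and reported as confirmed after pooled CDP had failed. The sentence comes after the general stop rule and uses if-and-only-if language, so a reader might take it as the specific rule that overrides the general one.

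At stake are up to three confirmatory claims and control of family-wise error at 0.05. A second worry is that the both-studies condition for CDP appears only in the SAP. If the sister study missed its primary endpoint, item 1 or item 2 while pooled CDP had p<0.05, the SAP would call CDP descriptive, whereas the protocol text alone would call it significant.

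**Working it through.** **Inputs.** Each test is at two-sided 0.05 (Protocol 8.9.2; SAP 2.4). The order and the stop rule are as above. NEDA power P and the within-study correlation w between test statistics are not in the documents; both are assumptions, shown over ranges.

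**1. The plan's own figure.** Suppose the primary and items 1 and 2 have real effects and are always significant, and CDP is null. Under the stop rule a false claim on CDP or on a later null endpoint requires CDP to be rejected, so the error is P(reject CDP) = 0.05. Simulation of the SAP rule gives 0.0498 to 0.0501 for w from 0 to 0.9. The stated 0.05 is reproduced.

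**2. The bypass reading, NEDA real, CDP and SDMT null.** NEDA contains relapses and MRI lesions, so a real effect on NEDA is the natural case when the primary and items 1 and 2 are real. An error now occurs if CDP is rejected, or if NEDA and SDMT are both rejected. With independent tests:

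error = 1 − 0.95 × (1 − 0.05P)

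- P = 0.3: 1 − 0.95 × 0.985 = 0.0643
- P = 0.8: 1 − 0.95 × 0.96 = 0.0880
- P = 0.9: 1 − 0.95 × 0.955 = 0.0928
- P = 1.0: 1 − 0.95 × 0.95 = 0.0975

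With correlation, pooled CDP is modelled as the sum of two equal-sized studies' statistics divided by √2, so its correlation with a single-study test is w/√2. Simulation with 2,000,000 draws (the w = 0 column is exact):

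| NEDA power | w = 0 | 0.3 | 0.5 | 0.7 | 0.9 |
|---|---|---|---|---|---|
| 0.3 | 0.064 | 0.065 | 0.067 | 0.069 | 0.068 |
| 0.8 | 0.088 | 0.085 | 0.080 | 0.074 | 0.068 |
| 1.0 | 0.0975 | 0.096 | 0.094 | 0.091 | 0.086 |

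**3. The bypass reading, CDP and NEDA both null.** At independence the error is 1 − 0.95² = 0.0975. If the two test statistics have correlation 0.3, 0.5, 0.7 or 0.9, it is 0.0951, 0.0907, 0.0835 or 0.0704.

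**4. Global null.** The primary gate holds the error at or below 0.05 on either reading.

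**5. Which reading the text supports.** The exception clause gives its own reason: CDP is analysed at the pooled level. The sentence before it is solely about pooling. Read this way, the exception concerns which data are used and leaves the order alone, which agrees with the stop rule earlier in the same section, with Protocol 2.2 and with the SAP. The bypass reading contradicts all three.

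**6. The both-studies condition.** Within this study, the primary, item 1, item 2 and pooled CDP form a fixed sequence of 0.05 tests. Requiring the sister study's results as well can only remove claims, so leaving that condition out of the protocol does not raise the error above 0.05.

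**The case for a change.** The strongest case for a change is that the protocol disagrees with itself before the SAP is opened. Deference to the SAP limits the harm but leaves the sentence in place, and one line would cure it. A clarification before unblinding is also cleaner than one made afterwards. It stands that the sentence is loosely worded and that the bypass reading, if anyone used it, would not hold 0.05.

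What does not stand is that a result depends on it. SAP version 3.0 bears the same date as protocol version 5.0 (04 September 2020), was written for that version and states the gate for items 4 to 6 outright. An analyst would have to set aside the SAP and the opening of 8.9.2 to go wrong.

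Nor would an edit be pure alignment. The SAP does not spell out whether items 4 to 6 proceed here when pooled CDP has p<0.05 but is non-confirmatory because the sister study missed an earlier gate. New wording that made them depend on a confirmatory CDP result would settle a question that the SAP text leaves open. The SAP's testing-sequence figure, not reproduced in the text available, may already answer it. Either answer keeps within-study error at or below 0.05, since items 4 to 6 would still require pooled CDP to have p<0.05.

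Item 3 in SAP 2.4.3.1 names this study as its own pooling partner. That is a clerical slip, and the footnote to the same list names both studies correctly.

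**Conclusion.** The wording is an editorial inconsistency and calls for no change to the plan. The stop rule is explicit in three places, and the governing SAP continues past CDP only when CDP is significant, so the hierarchy as planned has family-wise error of 0.05 and no excess. The figures of 0.064 to 0.0975 describe a reading that the rest of the plan excludes. They rest on assumed NEDA power (0.3 to 1.0), assumed correlations (0 to 0.9), equal-sized studies, real effects on the primary and items 1 and 2, and null effects on CDP and SDMT. The both-studies condition is a detail that the protocol leaves to the SAP, and its absence from the protocol does not inflate error within this study. Rewording the sentence would change no analysis and no reported conclusion for an analyst who follows the SAP.
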